7.4.1. Adverse Events

AEs should be monitored from the time of consent through 30 days after the last dose of study drug (both CMP-001 and pembrolizumab). Pretreatment AEs related to study procedures will be monitored from informed consent until the first dose of study drug (W1D1). After the subject is enrolled, all AEs will be captured on the eCRF.

See Section [8.3](#) for a full description of the collection and reporting of AEs during this study.

7.5. 30-Day Follow-Up Contact

The 30-Day Follow-up contact is a safety follow-up visit that should be conducted in the study clinic or via phone. The subject should be questioned for any new AEs, resolution of prior AEs, and use of concomitant medications, including other cancer treatments. No other safety assessments are required unless the Investigator identifies a new safety concern that requires further follow-up.

7.6. Posttreatment Follow-Up

Subjects who discontinue study treatment and transition into PTFU will continue to have assessments collected per the time points specified in the Schedule of Assessments ([Table 1](#)). Post treatment follow-up disease assessments will continue until disease progression, initiation of another cancer treatment, death, lost to follow-up, withdrawal of consent, or End of Clinical Trial.

7.7. Long-Term Survival Follow-Up

Subjects who discontinue study treatment and PTFU, will be contacted by the site according to the Schedule of Assessments ([Table 1](#)) for LTSFU, which will continue until death, withdrawal of consent, lost to follow-up, or End of Clinical Trial.

8. SAFETY DATA COLLECTION, RECORDING, AND REPORTING

8.1. Adverse Events

8.1.1. Definition of an Adverse Event

An AE is an untoward or medical occurrence associated with the use of study drug (active or placebo drug, biologic, or device) in clinical investigation subjects, which does not necessarily have a causal relationship with the study drug. An AE can therefore be any unfavorable and unintended symptom, sign, disease, condition, or test abnormality whether or not considered related to study drug ([Appendix C](#)). Adverse events that do not meet the definition for an SAE are considered non-SAEs.

Adverse events should be recorded upon first occurrence and followed until resolution. A persistent AE is continuous and does not resolve between Q3W dosing visits. The AE is documented only once unless the grade becomes more severe. If the grade becomes more severe the AE must be reported again with the new grade. Any recurrent AE should be reported as new AE.

Adverse events include:

- Changes in health status described by the subject or signs observed by the Investigator or medical staff.
- Test abnormalities (e.g., laboratory tests) that result in an alteration in medical care (diagnostic or therapeutic) and/or are considered clinically significant by the Investigator.

Disease progression, and associated hospitalizations, are not considered an AE or SAE in this study.

Abnormalities present at Baseline will be recorded as medical history and will only be considered AEs if they reoccur after resolution or worsen during the study.

8.1.2. Definition of a Serious Adverse Event

An SAE is any AE that fulfills 1 of the criteria outlined in Section [8.1.2](#).

Table 3: Criteria for Determination of Serious Adverse Events

Death	An adverse event (AE) that results in death. NOTE: In this study, deaths due to Disease Progression are not to be reported as SAEs.
Life-threatening AE	An AE that places the subject, in the view of the Investigator, at immediate risk of death from the AE as it occurred (i.e., does not include an AE that had it occurred in a more severe form, might have caused death).
Required or prolonged inpatient hospitalization ^a	An AE that results in an initial inpatient hospitalization or prolongs an existing hospitalization of the subject. If a subject is hospitalized as part of the clinical use of the study drug, a period of normal hospitalization will be outlined in the protocol or by the judgment of the Investigator. Hospitalizations longer than this period will be prolonged hospitalizations.
Persistent or significant disability/incapacity	An AE that results in a substantial disruption of a subject's ability to conduct normal life functions.
Congenital anomaly/birth defect	A congenital anomaly/birth defect that occurs in the offspring of a subject exposed to the study drug.
Important medical event	An AE which may not result in death, be life-threatening, or require hospitalization may be considered an SAE when, based upon appropriate medical judgment, the event may jeopardize the subject and may require medical or surgical intervention to prevent 1 of the outcomes listed above, in the opinion of the Investigator.

a. Planned hospital admissions or surgical procedures for elective procedures or for an illness or disease that existed before the W1D1 visit will not be captured as SAEs. If planned admissions or procedures occur at a time other than what was planned (i.e., due to an exacerbation in the preexisting illness or disease), they should be reported as SAEs.

[Appendix C: CTCAE version 5.0](#)

Examples of “important medical events” include allergic bronchospasm requiring intensive treatment in an emergency room or at home, blood dyscrasias or convulsions that do not result in inpatient hospitalization, or the development of drug dependency or drug abuse.

Medical and scientific judgment should be exercised in deciding whether expedited reporting is appropriate in other situations, such as with important medical events described above.

Events that meet SAE criteria must be recorded and reported regardless of expectedness or assessed association with study drug.

Hospitalization due solely to the progression of underlying HNSCC should not be reported as an SAE.

8.1.3. Definition of a Treatment-Emergent Adverse Events

A TEAE is defined as an AE that started or worsened in severity on or after the date that study drug was first administered (W1D1) until 30 days after the last dose of study treatment.

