Procedure or Assessment	Screening (Day -30 to Day -1)	W1D1	W2D1	W4D1	W4D2	Q3W (W7D1, W10D1, etc.)	End of Treatment (EOT) ^a	30-Day Safety Follow-up (30DFU) ^b	Posttreatment Follow-up (PTFU) ^c (Q3mo)	Long-Term Survival Follow-up (LTSFU) ^d (Q3mo)
Visit Windows	n/a	n/a	-2/+5d	+3d	n/a	± 3d	+7d	+7d	± 2 weeks	± 4 weeks
CMP-001 Injection (Dose Number) ^e		1 SC/IT	2	3		4+				
Pembrolizumab Dosing (Dose Number) ^f		1		2		3+				
Thyroid Function Tests ^l	X			X		X	X			
Autoimmune Laboratory Panel ^l	X						X			
Pregnancy Test and Follicle Stimulating Hormone ^l	X	X		X		X	X			
Exploratory Biomarker Sampling ^m		X		X	X	W7D1				
Exploratory Sampling for Pharmacokinetics ^m		X		X	X	W7D1				
Tumor Biopsy (known PD-L1 status) ⁿ	X					W7D1				
Blood Sampling for Cytokine and Complement ^o		X		X		W7D1				
Disease Assessment (Radiographic Imaging) ^p	X					W10D1 Q9W	X		X	
Disease Assessment (CNS Imaging) ^p	X					W10D1 Q9W	X		X	
Photographic Imaging ^q	X					W10D1 Q9W	X		X	
30-Day Follow-Up (Office or Phone Call)								X		
Long-Term Survival Follow-up Phone Call										X

Abbreviations: 30DFU = 30-day follow-up; CNS = central nervous system; CPS = combined positive score; D = day; ECG = electrocardiogram; ECOG = Eastern Cooperative Oncology Group; EOT = end of treatment; FSH = follicle stimulating hormone; HPV = human papillomavirus; iRECIST = immunotherapy Response Evaluation Criteria in Solid Tumors; LTSFU = long-term survival follow-up; MRI = magnetic resonance imaging; PTFU = posttreatment follow-up; RECIST = Response Evaluation Criteria in Solid Tumors; Q3W = every 3 weeks; W = week; WOCBP = women of child bearing potential.

a. EOT assessments to be performed within 7 days following subject discontinuation from study treatment. Removal of a subject from CMP-001 treatment is defined as the time in which the Investigator decides to discontinue study treatment. If a subject has CMP-001 dosing withheld for more than 3 consecutive doses for any reason during the Q3W dosing period, resumption of treatment must be discussed with the Medical

Amendment 2 (Version 3.0)

14 January 2022

13

Confidential

Monitor; otherwise, the subject will be discontinued from study treatment and will have all EOT assessments performed. End of Treatment occurs once the subject discontinues administration of CMP-001. Subjects can continue to receive pembrolizumab as standard of care but will no longer be considered in study treatment.

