- h. Vital signs include measurement of blood pressure (systolic and diastolic blood pressure), respiratory rate, heart rate, and body temperature. Blood pressure and heart rate should be taken in the seated position following ≥ 3 minutes of rest. For the first 4 CMP-001 dosing visits (W1D1, W2D1, W4D1, and W7D1), vital signs must be collected before the CMP-001 injection and at 30 (± 15)-minute intervals for 4 hours after CMP-001 injection. Starting at W10D1, observation periods may be reduced to a minimum of 1 hour following CMP-001 injection at the Investigator's discretion based on the AE profile of the individual subject. When vital signs are scheduled at the same time as collection of a blood sample, the vital sign measurements should be obtained before the scheduled phlebotomy. If a study visit occurs where only pembrolizumab is administered, vital signs must be collected before the start of the pembrolizumab infusion.

NOTE: Oxygen saturation is not a required parameter to be collected. Sites are to capture oxygen saturation every time an AE of hypoxia or cytokine release syndrome is reported for a subject.

- i. Adverse events will be assessed continually from time of consent through 30 days after the last dose of study drug for all subjects. Subjects who discontinue CMP-001 but remain on treatment with pembrolizumab will continue to have AEs collected according to this schedule until 30 days after the last dose of pembrolizumab.
- j. Concomitant medications will be assessed continually from time of consent through 30 days after the last dose of study drug. Treatment medications for study-related AEs that occur through 30 days after the last dose of study drug will be collected during the 30-Day Safety Follow-Up period.
- k. 12-lead ECGs will be obtained at Screening, before the W1D1 CMP-001 injection, and at EOT. ECG parameters will include heart rate and PR, QRS, QT, and QT corrected for heart rate (QTc) intervals. ECGs will be performed after the subject has been resting in supine or semi-supine position for at least 5 minutes. When an ECG is scheduled at the same time as a blood sampling, the ECG reading should be obtained before the scheduled blood sampling.

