8.3. Procedures for Recording and Reporting Adverse Events

The Investigator is required to report to the Sponsor or its representatives all AEs that occur during the clinical trial (Title 21 Code of Federal Regulations [CFR] Part 312.64[b] and ICH E6 entitled “Guideline to Good Clinical Practice”) (ICH E6). At each study visit, subjects will be evaluated for new AEs and the status of existing AEs. TEAEs observed from the time of consent until 30 days after the last dose of study drug (both CMP-001 and pembrolizumab) are to be recorded on the AE page of the eCRF.

The date, time of onset, resolution, determination of seriousness, severity, action taken, outcome and relationship to CMP-001 and pembrolizumab will be recorded for all AEs. AEs starting more than 30 days after the last dose of study drug should not be recorded on the AE eCRF unless they are considered to be related to study treatment.

All AEs and SAEs experienced by a subject will be recorded on the appropriate eCRF. In addition, for all SAEs a paper SAE Report Form will be completed and submitted to IQVIA Biotech Safety preferably via email to: [REDACTED] or by fax to [REDACTED]

[REDACTED] as back up within 24 hours of awareness. Information including a detailed description of the event; date and time (24-hour clock) of event onset and resolution; determination of seriousness, severity, corrective treatment, outcome, relationship to study drug; and action taken regarding the study drug will be recorded. Vital signs, laboratory results, and other safety assessments noted in Section 7.4 will be recorded as AEs if they are determined to be clinically significant findings in the opinion of the Investigator. When possible, a diagnosis should be recorded as an AE, rather than symptoms or isolated laboratory abnormalities related to the diagnosis. A medical or surgical procedure is not an AE; rather the condition leading to the procedure should be recorded as the AE. If the condition is not known, the procedure must be recorded as an AE instead. Similarly, death is not an AE, but is rather the outcome of the AE(s) that resulted in death. If the AE(s) leading to death are not known, then death must be reported as an AE.

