The number of subjects with dose modifications (e.g., Drug Delayed, Drug Withheld, Drug interrupted, Dose Reduced, Drug Permanently Withdrawn) with the reasons will also be summarized by study drug.

Additionally, subgroup analysis of drug dosing and intensities for subjects by schedule will also be performed. Listings will be provided with the information from the study drug administration eCRFs for CMP-001 and Pembrolizumab, including date and time of each dose, route of administration, dose administered, location of each injection, and the volume injected into each tumor at each dosing visit.

Regeneron Pharmaceuticals Inc. / Protocol: CMP-001-007
IQVIA Biotech (Confidential) Project # SZA56629

B. Adverse Events

Adverse events should be recorded upon first occurrence and followed until resolution. A persistent AE is continuous and does not resolve between Q3W dosing visits; and should be documented only once unless the grade becomes more severe. If the grade becomes more severe, the AE must be reported again with the new grade. Any recurrent AE should be reported as new AE each time the AE occurs. Worsening of an ongoing TEAE (i.e., an increase to higher grade) should be recorded as a new AE. Ongoing AEs that decrease in severity/grade should not be captured as new AEs.

According to Protocol section 8.1.1, disease progression, and associated hospitalizations and deaths, are not considered an AE or SAE in this study.

Medical occurrences that begin before start of study treatment should be recorded on the Medical History/Current Medical Conditions section of the eCRF, not the AE section.

Adverse events starting more than 30 days after the last dose of study treatment should not be recorded on the AE eCRF unless they are related to study treatment.

Serious adverse events and AEs resulting in discontinuation will be followed until 1 of the following occurs:

- The event resolves
- The event stabilizes
- The event returns to a Baseline value if a Baseline value is available
- The event can be attributed to agents other than the study treatment or to factors unrelated to study conduct
- The Investigator and Medical Monitor agree that follow-up is no longer necessary

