Adverse event (AE) data are available to the Sponsor from two sources, the eCRFs and the Serious Adverse Event (SAE) paper forms and corresponding SAE narratives. While reconciliation will be performed to ensure consistency between the two types of data, the production of data summaries and listings will be based on the data collected on the eCRF.

Treatment-emergent adverse event (TEAE)

Pretreatment AEs are AEs that occur from the time of informed consent up to the first dose of study treatment (W1D1). A treatment-emergent adverse event (TEAE) is defined as an AE that started or worsened in severity on or after the date that study treatment was first administered (W1D1) until 30 days after the last dose of

Regeneron Pharmaceuticals Inc. / Protocol: CMP-001-007
IQVIA Biotech (Confidential) Project # SZA56629

study treatment. AE data collection also ceases at the time a new cancer treatment is started per protocol section 8.3, whichever occurs first.

Treatment-emergent adverse events will be coded using MedDRA (version 23.1) and data will be summarized for the Treated Analysis Set. The number and percent of subjects reporting each TEAE will be summarized, as well as the number of TEAEs. A subject with 2 or more TEAEs within the same level of summarization (i.e., system organ class or preferred term) will be counted only once in that level using the most severe event or most related (for the relationship to study treatment tables).

AEs are graded using Common Terminology Criteria for Adverse Events (CTCAE) Version 5.0. AE summaries may include summaries for all AEs and by the maximum CTCAE grade for the item being summarized (i.e., SOC or PT). In these cases, the outputs will include a row for All Grades as well as rows for the 5 potential CTCAE grades: Grade 1 (Mild), Grade 2 (Moderate), Grade 3 (Severe), Grade 4 (Life threatening or disabling), or Grade 5 (Death).

If grade is missing for a TEAE, the event will be counted as grade 3=severe in the TEAE summary tables. If relationship is missing for a TEAE, the event will be counted as related in the TEAE summary tables. Therefore, related AEs include those which are definitely, probably and possible related and those with missing relationship.

A TEAE summary table will be generated including the following (N (%)):

- Subjects with TEAEs
- Subjects with TEAEs of grade 3 or higher
- Subjects with TEAEs Related to CMP-001 and/or Pembrolizumab
- Subjects with CMP-001-related TEAEs

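### Related AEs starting more than 30 days after the last dose are recorded but fall outside the TEAE incidence tables, and the documents contradict themselves on whether continued pembrolizumab keeps the TEAE window open

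*Protocol*

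**What the plan says.** Protocol 8.1.3 runs treatment emergence from the day study drug was "first administered (W1D1) until 30 days after the last dose of study treatment". SAP IX.B adopts the same window, again tied to study treatment, for AEs that are new in it or have "worsened in severity on or after the date that study treatment was first administered (W1D1) until 30 days after the last dose of". Neither makes an exception for related events.

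The recording rule is wider. Under Protocol 8.3, AEs that start more than 30 days after the last dose "should not be recorded on the AE eCRF unless they are considered to be related to study treatment". SAP IX.B repeats that they "should not be recorded on the AE eCRF unless they are related to study treatment". Related late events therefore go on the form.

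On what counts as treatment after CMP-001 stops, note a to Protocol Table 1 says: "Subjects can continue to receive pembrolizumab as standard of care but will no longer be considered in study treatment". Note i to the same table says that subjects who stop CMP-001 but stay on pembrolizumab "will continue to have AEs collected according to this schedule until 30 days after the last dose of pembrolizumab".

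The AE incidence tables in Protocol 9.6.1 and SAP IX.B are built on TEAEs, with the partial exception of the SAE tables discussed below.

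**The concern.** Safety and tolerability of the combination is the first secondary objective. The protocol recognises immune-mediated toxicity and deliberately collects related events with late onset. A definition that then removes those events from the tables of related, Grade 3 or higher and fatal TEAEs can only lower the reported incidences.

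The second problem is reproducibility. If study treatment ends with CMP-001, the TEAE window closes while the subject may still be receiving pembrolizumab and having AEs recorded. If it ends with the last dose of either drug, the window stays open. Two programmers working from the same text could produce different TEAE counts.

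**Working it through.** The plan states no figure on this point, so there is nothing to reproduce. The check compares passages and date windows.

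**Step 1. Late related AEs.** Take an AE judged related, with onset on day 31 or later after the last dose of both drugs.
- Recorded? Yes (Protocol 8.3; SAP IX.B).
- A TEAE? No (Protocol 8.1.3; SAP IX.B).

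This result does not depend on which drug sets the clock. The gap is open-ended, because the recording rule for related events has no closing date in Protocol 8.3.

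**Step 2. Where such an event would appear.**

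| Output | Late related AE included? |
|---|---|
| SAP IX.B tables of all, related and Grade 3 or higher TEAEs | No |
| SAP IX.B row and table for fatal TEAEs | No |
| Protocol 9.6.1 SAE summary | Yes; no treatment-emergent limit is stated |
| SAP IX.B overall summary, count of subjects with SAEs | No; labelled treatment-emergent |
| SAP IX.B SAE tables by SOC and preferred term | Unclear; listed under a TEAE heading, but the titles carry no such limit |
| SAP IX.B by-subject AE listing and separate SAE listing | Yes; not restricted to TEAEs |
| SAP IX.C death summary | Yes if fatal; covers all deaths on study or in follow-up |

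A late related event that is neither serious nor fatal is therefore in no incidence table.

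**Step 3. Two uses of study treatment.**
- Ends with CMP-001: Table 1 note a.
- Includes pembrolizumab, or runs to the last drug: Table 1 note i (AE collection to 30 days after the last pembrolizumab dose); Protocol 7.4.1 and 8.3 (30 days after the last dose of both drugs); Protocol 8.2.2 (both drugs are components of the study treatment); SAP VI.C (imputed AE stop dates capped at 30 days after the end of treatment with the last study drug received).

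The situation can arise: Protocol 4.5 allows CMP-001 alone to be stopped after a confirmed CR or iCR, once the subject has had at least 24 weeks on both drugs and meets the post-response dosing condition.

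**Step 4. Size of the gap for AEs on continued pembrolizumab.** Stop weeks are assumed; days count from first dose. Window end = 7 × stop week + 30.

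| CMP-001 stops | Pembrolizumab stops | TEAE window ends (note a reading) | AE collection ends (note i) | Gap |
|---|---|---|---|---|
| Week 24 | Week 24 | 168 + 30 = 198 | 198 | 0 days |
| Week 24 | Week 52 | 198 | 364 + 30 = 394 | 196 days |
| Week 52 | Week 104 | 394 | 728 + 30 = 758 | 364 days |
| Week 24 | Week 104 | 198 | 758 | 560 days = 80 weeks |

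On the both-drugs reading the gap is 0 in every row.

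**Step 5. Effect on a table row.** SAP II.C gives 24 treated subjects, so one omitted subject moves a row by 100/24 = 4.2 percentage points. The documents give no rate for late events. If a proportion p of subjects had one, the expected number is 24p and the chance of at least one is 1 − (1 − p)^24:

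| Assumed p | Expected subjects | Chance of at least one |
|---|---|---|
| 2% | 0.5 | 38% |
| 5% | 1.2 | 71% |
| 10% | 2.4 | 92% |
| 15% | 3.6 | 98% |

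**The case against.** **A fixed 30-day window is a legitimate choice.** It gives every subject the same ascertainment. Protocol 8.3.4 says investigators need not actively seek AEs in former subjects after follow-up, so late events are partly spontaneous reports. This stands as a reason not to pool late events with the fixed-window counts. It does not justify giving them no incidence table.

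**The events do not vanish.** A reader might infer that they are lost from every planned AE summary, or that a late related death goes uncounted. The documents do not support that. SAP IX.C summarises all deaths with primary cause, the Protocol SAE summary has no treatment-emergent limit, and the AE and SAE listings are not restricted to TEAEs. Two qualifications remain. SAP I.B says the SAP governs where the documents differ, and its SAE tables have unclear scope. A late related death would also appear in the death summary but not in the fatal-TEAE outputs, with no explanation for the difference.

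**The pembrolizumab exclusion rests on one footnote.** A reader might infer from note a that AEs on continued pembrolizumab are definitely excluded. The passages in Step 3 point the other way, and Protocol 8.3 even applies the term TEAE to the two-drug window. What stands is a contradiction to be reconciled. The 80-week case also borrows the two-year limit on study treatment to date the end of pembrolizumab, although under note a that pembrolizumab is no longer study treatment; Week 104 is therefore an assumption.

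**All analyses are descriptive and exploratory.** That is true and limits the consequence, but the safety tables are among the results this curtailed study will report.

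**Conclusion.** The point holds in two parts of different strength.

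- Established in both documents: related AEs starting more than 30 days after the last dose are recorded but excluded from the TEAE incidence tables. If neither serious nor fatal, they appear only in listings.
- Contradictory: whether AEs on pembrolizumab continued after CMP-001 are TEAEs. The gap runs from zero to 80 weeks in the assumed cases, depending on which passage is followed.

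Each omitted subject costs 4.2 percentage points, and omission can only lower an incidence. How many subjects are affected cannot be derived from the documents; the 38% to 98% range rests on assumed rates of 2% to 15%. The primary endpoint is untouched. This should be corrected, but it does not threaten the study's main result.

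**What to change.** 1. In Protocol 8.1.3 and SAP IX.B, define the TEAE window as running from first dose to 30 days after the later of the last CMP-001 or last pembrolizumab dose.
2. Report related AEs starting after that window in a separate incidence table or as flagged rows (all related, Grade 3 or higher, serious, fatal), so they are visible but not mixed with fixed-window events.
3. State whether the SAP IX.B SAE tables by SOC and preferred term are limited to treatment-emergent events.
4. Reconcile the passages that set AE windows, for AE analysis only: Table 1 notes a and i; Protocol 7.4, which has a second TEAE definition starting at consent with no closing date; Protocol 7.4.1 and 8.1.3; Protocol 8.3, which applies the term TEAE from consent; and SAP IX.B. SAP IX.B also ends AE collection at a new cancer treatment, citing Protocol 8.3, whose text has no such rule. Changing only 8.1.3 and the SAP would leave the protocol inconsistent.

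None of this alters dosing or discontinuation rules. The cost is wording, one derivation flag and one table, since the protocol already requires the data to be recorded. The downsides are slightly less favourable incidences and a late-event table that partly reflects spontaneous reporting and should be footnoted as such.
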